9.3 Processing and Storage

Tissue samples will be sent to Siteman Cancer Center Tissue Procurement Core (TPC) and processed according to TPC standard operating procedures. Biospecimens will be cryopreserved and stored for future analysis.

10.0 STUDY CALENDAR

Screening/baseline evaluations are to be conducted within 2 weeks prior to start of protocol therapy. Scans and x-rays must be done no more than 4 weeks prior to the start of the protocol therapy. Cycles are 21 days long. There is a +/- 3 day window for all assessments and procedures.

	Screening	Baseline	C1 D1	C2 D1	After Cycle 2	D1 of subsequent cycles	End of every 2 cycles	EOT	F/U ³
Informed consent	X								
H&P, ECOG PS	X			X		X		X	
CBC	X		X	X		X			
CMP	X		X	X		X			
PTT/aPTT, INR	X								
TSH ⁶	X		X						
Hepatitis B and C test	X								
Pregnancy test ¹	X								
Urinalysis	X		X	X		X			
CT scan	X						X		
Ramucirumab			X	X		X			
Atezolizumab			X	X		X			
Research blood		X		X					
Archival tumor		X ⁵							
Fresh biopsy		X ⁵			X ⁴				
Survival									X
AE assessment		X	-----						X ²

1. For women of childbearing potential only

2. For 30 days after end of treatment

3. Every 3 months for 2 years; may be done by phone.

4. When feasible, the biopsy will follow CT scan performed between Cycles 2 and 3

5. When available, archival biopsy tissue will be used for a baseline biopsy. If baseline tissue is not available, the patient will undergo a baseline biopsy prior to initiation of the trial.

6. Reflex to free T3, free T4.

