1.0 BACKGROUND AND RATIONALE

1.1 Non-Small Cell Lung Cancer (NSCLC)

Lung cancer remains the leading cause of cancer-related death, with an estimated 1.6 million deaths per year ¹. In the United States, the American Cancer Society estimates that there will be approximately 250,000 new cases of lung cancer and 158,000 deaths in 2018 ². Approximately 85% of patients with lung cancer have a group of histological subtypes, collectively known as non-small cell lung cancer (NSCLC) ³. The majority of patients with NSCLC present with stage IV disease due to distant metastases or malignant pleural effusion and are treated with palliative intent ⁴. Even among patients undergoing surgery with curative intent, a high percentage of tumors recur, with 5-year overall survival (OS) ranging from 83% in stage IA to 36% in stage IIIA ⁵. Patients with metastatic NSCLC and no targetable oncogenic alterations usually have a poor prognosis, with low responses to the initial platinum-based chemotherapy and virtually universal relapse ⁶. Immune checkpoint blockers (ICBs) have revolutionized the treatment of NSCLC, with the three approved drugs (nivolumab, pembrolizumab and atezolizumab) being more effective than docetaxel in randomized clinical trials ⁷⁻¹⁰. Nevertheless, the benefit is restricted to a small percentage of patients, with objective response rates of less than 20% and median progression-free survival (PFS) ranging from 2.3 to 3.9 months.

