2.2 Secondary Objectives

1. To determine the overall survival (OS) for the combination of ramucirumab and atezolizumab in patients with NSCLC who have previously received an ICB.
2. To determine the progression-free survival (PFS) for the combination of ramucirumab and atezolizumab in patients with NSCLC who have previously received an ICB.
3. To determine clinical benefit rate (CBR) for the combination of ramucirumab and atezolizumab in patients with NSCLC who have previously received an ICB. CBR is defined as the percentage of patients who have achieved responses or stable disease.
4. To evaluate toxicity and tolerability of this combination as measured by NCI-CTCAE version 5.0.

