7. Arterial or venous thromboembolic event, including but not limited to myocardial infarction, transient ischemic attack, cerebrovascular accident, or unstable angina, within 6 months prior to enrollment.

8. Uncontrolled or poorly controlled hypertension (> 160 mmHg systolic or > 100 mmHg diastolic for > 4 weeks) despite standard medical management.
9. Gastrointestinal perforation, and/or fistula, or risk factors for perforation within 6 months prior to enrollment.
10. Grade 3 or 4 gastrointestinal bleeding within 3 months prior to enrollment.
11. History of autoimmune disease, including but not limited to systemic lupus erythematosus, rheumatoid arthritis, inflammatory bowel disease, vascular thrombosis associated with antiphospholipid syndrome, Wegener's granulomatosis, Sjögren's syndrome, Bell's palsy, Guillain-Barré syndrome, multiple sclerosis, autoimmune thyroid disease, vasculitis, or glomerulonephritis.

Note: Patients with a history of autoimmune hypothyroidism on a stable dose of thyroid replacement hormone are eligible. Patients with controlled type 1 diabetes mellitus on a stable insulin regimen are eligible.

12. History of idiopathic pulmonary fibrosis, pneumonitis (including drug-induced), organizing pneumonia (i.e., bronchiolitis obliterans, cryptogenic organizing pneumonia, etc.), or evidence of active pneumonitis on screening chest CT scan.
13. Hemoptysis (defined as bright red blood or \geq ½ teaspoon) within 2 months prior to Cycle 1 Day 1 or with radiographic evidence of intratumor cavitation or radiologically documented evidence of major blood vessel invasion or encasement by cancer.
14. Serious or non-healing wound, ulcer, or bone fracture within 28 days prior to Cycle 1 Day 1.
15. Undergone major surgery within 28 days prior to Cycle 1 Day 1, or minor surgery/subcutaneous venous access device placement within 7 days prior to Cycle 1 Day 1, or has elective or planned major surgery to be performed during the course of the clinical trial.
16. Known clinically significant liver disease, including cirrhosis at a level of Child-Pugh B or worse, cirrhosis (any degree) with a history of hepatic encephalopathy or clinically meaningful ascites resulting from cirrhosis (defined as ascites from cirrhosis requiring diuretics or paracentesis), fatty liver, and inherited liver disease.

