5.5 Duration of Therapy

If at any time the constraints of this protocol are considered to be detrimental to the patient's health and/or the patient no longer wishes to continue protocol therapy, the protocol therapy should be discontinued and the reason(s) for discontinuation documented in the case report forms.

In the absence of treatment delays due to adverse events, treatment may continue indefinitely or until one of the following criteria applies:

- Documented and confirmed disease progression
- Death
- Adverse event(s) that, in the judgment of the investigator, may cause severe or permanent harm or which rule out continuation of study drug
- General or specific changes in the patient's condition render the patient unable to receive further treatment in the judgment of the investigator
- Suspected pregnancy
- Serious non-compliance with the study protocol
- Lost to follow-up
- Patient withdraws consent
- Investigator removes the patient from study
- The Siteman Cancer Center decides to close the study

Patients who prematurely discontinue treatment for any reason will be followed as indicated in the study calendar.

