6.2 Dose Modifications for Atezolizumab

Atezolizumab dose reduction is not allowed. However, study treatment may be temporarily

suspended in patients experiencing toxicity considered to be related to study treatment for up to 60 days after the last dose if they experience toxicity that require a dose to be withheld. If atezolizumab is withheld because of toxicity for > 60 days after the last dose, then the patient will be discontinued from atezolizumab treatment and will be followed for safety and efficacy.

Recommendations for dosage modifications are provided in the table below:

Adverse Reaction	Severity (by CTCAE Grade)	Dosage Modifications
Pneumonitis	2	Withhold dose until grade 1 or resolved and corticosteroid dose \leq 10 mg/day (or equivalent)
	3 or 4	Permanently discontinue
Hepatitis	AST or ALT 3-5 x ULN or total bilirubin 1.5-3 x ULN	Withhold dose until grade 1 or resolved and corticosteroid dose \leq 10 mg/day (or equivalent)
	AST or ALT > 5 x ULN or total bilirubin > 3 x ULN	Permanently discontinue
Colitis or diarrhea	2 or 3	Withhold dose until grade 1 or resolved and corticosteroid dose \leq 10 mg/day (or equivalent)
	4	Permanently discontinue
Endocrinopathies (including but not limited to hypophysitis, adrenal insufficiency, hyperthyroidism, and type 1 diabetes mellitus)	2, 3, or 4	Withhold dose until grade 1 or resolved and clinically stable on hormone replacement therapy
Other immune-mediated adverse reactions involving a major organ	3	Withhold dose until grade 1 or resolved and corticosteroid dose \leq 10 mg/day (or equivalent)
	4	Permanently discontinue
Infections	3 or 4	Withhold dose until grade 1 or resolved
Infusion-related reactions	1 or 2	Interrupt or slow the rate of infusion
	3 or 4	Permanently discontinue
Persistent grade 2 or 3 adverse reaction (excluding endocrinopathies)	2 or 3 that does not recover to 0 or 1 within 60 days after last dose	Permanently discontinue
Inability to taper	Inability to	Permanently discontinue

corticosteroid	reduce to ≤ 10 mg/day (or equivalent) within 60 days after last dose	
Recurrent grade 3 or 4 adverse reaction	Recurrent grade 3 or 4	Permanently discontinue

Dose interruptions for reasons other than toxicity (e.g., surgical procedures) may be allowed, with PI approval. The PI will determine the acceptable length of interruption.

Patients who discontinue atezolizumab must come off study.

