7.0 REGULATORY AND REPORTING REQUIREMENTS

The entities providing oversight of safety and compliance with the protocol require reporting as outlined below. Please refer to Appendix B for definitions and Appendix C for a grid of reporting timelines.

Adverse events will be tracked from start of treatment through 30 days after the last administration of study drug. All adverse events must be recorded on the toxicity tracking case report form (CRF) with the exception of:

- Baseline adverse events, which shall be recorded on the medical history CRF
- Laboratory adverse events that are not clinically significant

Refer to the data submission schedule in Section 11 for instructions on the collection of AEs in the EDC.

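### No thyroid test is scheduled after the first dose, although Section 6.2 advises withholding atezolizumab for grade 2 to 4 endocrinopathies, including hyperthyroidism

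*Combined protocol and SAP*

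**What the plan says.** In the Section 10.0 calendar the TSH row has marks under Screening and C1 D1. It is blank under C2 D1, After Cycle 2, D1 of subsequent cycles, End of every 2 cycles, EOT and follow-up. Its footnote reads "Reflex to free T3, free T4". The CBC, CMP and urinalysis rows of the same table are marked at Screening, C1 D1, C2 D1 and D1 of subsequent cycles.

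Section 6.2 introduces its dose-modification table with "Recommendations for dosage modifications are provided in the table below". One row covers "Endocrinopathies (including but not limited to hypophysitis, adrenal insufficiency, hyperthyroidism, and type 1 diabetes mellitus"). For grades 2, 3 or 4 it advises holding atezolizumab until the event has resolved or fallen to grade 1 and the patient is stable on hormone replacement.

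Three other provisions set the context:

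- **Duration.** Section 5.5 says "treatment may continue indefinitely or until one of the following criteria applies".
- **Eligibility.** A note in Section 3.2 says "Patients with a history of autoimmune hypothyroidism on a stable dose of thyroid replacement hormone are eligible".
- **Safety objective and recording.** The fourth secondary objective in Section 2.2 is "To evaluate toxicity and tolerability of this combination as measured by NCI-CTCAE version 5.0". Section 7.0 exempts from the toxicity form "Laboratory adverse events that are not clinically significant".

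**The concern.** Both drugs are first given on C1 D1 (Section 5.1), so the two scheduled TSH tests are in effect baseline values. Nothing scheduled later can be compared with them. A hold rule that names a thyroid disorder therefore has no scheduled thyroid test behind it for the whole of treatment, which has no fixed end.

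Two things are at stake. The first is patient safety: a clinically significant thyroid event could be recognised late. The second is the toxicity objective: if TSH is ordered at individual discretion, patients are not observed in the same way, and the thyroid entries in a 21-patient toxicity summary depend partly on who was tested. Because of the Section 7.0 exemption, only clinically significant events are in question. The primary endpoint and the 21-patient decision rule are not affected.

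**Working it through.** **1. Is the blank real?** The TSH row lines up with its neighbours. The on-treatment columns exist and are filled for CBC, CMP and urinalysis, so an extraction fault is unlikely. The footnote adds reflex analytes, not visits. The calendar's ±3-day window moves a visit but does not create one. No other section schedules TSH, free T3 or free T4. Scheduled TSH timepoints: 2. Scheduled after the C1 D1 visit: 0.

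**2. Do other hold rules have a scheduled test behind them?**

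| Rule | Where | Scheduled on-treatment test |
|---|---|---|
| AST, ALT and bilirubin thresholds | Section 6.2 | CMP on Day 1 of every cycle |
| Urine protein thresholds | Section 6.1.3 | Urinalysis on Day 1 of every cycle, which can prompt the 24-hour collection |
| Endocrinopathy, grade 2 to 4, hyperthyroidism named | Section 6.2 | No thyroid test |

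**3. How much exposure goes without a scheduled TSH?** The plan gives no figure to reproduce and no thyroid event rate, so the clinical effect cannot be sized. Exposure can be counted.

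Inputs:
- The cycle length is 21 days (Section 5.1).
- Time on treatment is assumed to be 2.3, 3.9 or 6 months. The first two values come from Section 1.1, which reports "median progression-free survival (PFS) ranging from 2.3 to 3.9 months" for checkpoint blockers. That is a different population and regimen, used here only as a stand-in. The 6-month case reflects Section 1.6.1, where 3 of the first 12 patients were still on treatment with PFS above 6 months.
- One month is 365.25/12 = 30.4375 days.

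Formula: Day 1 visits after C1 = floor(months × 30.4375 / 21), with no delays.

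- 2.3 months: 70.0 days; 70.0/21 = 3.33, so 3 visits (C2 to C4)
- 3.9 months: 118.7 days; 118.7/21 = 5.65, so 5 visits (C2 to C6)
- 6 months: 182.6 days; 182.6/21 = 8.70, so 8 visits (C2 to C9)

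Each of these visits draws CBC and CMP with no TSH scheduled. Treatment holds would lower the counts. Section 6.1 allows treatment to be held for at most 6 weeks; for toxicity, Section 6.2 allows atezolizumab to be suspended up to 60 days after the last dose.

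**4. What would testing every second cycle add?** Counting the odd-numbered cycles from C3 within those ranges:

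- 2.3 months: C3, 1 test
- 3.9 months: C3 and C5, 2 tests
- 6 months: C3, C5, C7 and C9, 4 tests

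**5. Whom would a change reach?** If the status described in Section 1.6.1 still holds, 3 patients on treatment plus 9 still to accrue = 12.

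**The case against.** The strongest reply is that clinical surveillance is already in place. History and physical is scheduled at C2 D1, on Day 1 of each later cycle and at EOT, AE assessment runs to 30 days after treatment, and any physician may order a TSH. The hold starts only at grade 2, and nothing in the documents shows that such an event would escape a visit every three weeks. This stands as a limit on the claim: late detection is a possibility, not a demonstrated consequence. It does not supply a scheduled test.

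Further points, and what remains of each:

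- **A management rule is not a duty to screen.** The same row names hypophysitis and adrenal insufficiency, and the calendar has no dedicated hormone test for those either. That is fair, and the documents do not contradict themselves. But TSH is a test the plan already chose to collect, twice, before any on-treatment value could exist.
- **The gain for the toxicity objective is thin.** Many abnormal TSH values would fall under the Section 7.0 exemption, and with no comparator, uneven testing biases no between-arm contrast. Both are true. Clinically significant events remain, and in a descriptive summary of 21 patients a few late or missed ones would show.
- **Known thyroid disease and prior exposure.** Patients admitted with autoimmune hypothyroidism are already on stable replacement, and every patient has had a checkpoint blocker, so baseline TSH is already a post-exposure value. This weakens the eligibility note as support. It does not replace measurement during treatment.
- **The interval is the reviewer's choice, and the effect is unsized.** Both are accepted.

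**Conclusion.** The point holds as a cheap improvement. Followed as written, the plan schedules two TSH tests by the first dosing day and none afterwards, while advising atezolizumab holds for a class of events that includes hyperthyroidism. Confidence is medium: the schedule is clear, but the clinical consequence cannot be quantified from the documents. What can be stated is exposure: 3, 5 or 8 later Day 1 visits without a scheduled TSH by 2.3, 3.9 or 6 months. This assumes 21-day cycles without delay and treats the quoted PFS figures as time on treatment. The conclusion is limited to scheduled laboratory surveillance and has no bearing on ORR, power or sample size.

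**What to change.** In the TSH row of Section 10.0, add a mark under D1 of subsequent cycles with a footnote limiting it to every second cycle (C3, C5, C7 and so on). Draw it with the CBC and CMP already due that day, and keep the free T3/free T4 reflex. Apply it to patients still on treatment and to those yet to enrol. The documents set no TSH interval; every second cycle is proposed because it matches the 6-week response assessment in Section 12.1.

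The cost is one assay about every 6 weeks (the 1, 2 or 4 tests per patient counted above) and an occasional reflex test, with no extra visit or draw. The calendar edit needs an IRB-approved amendment, and a missed TSH would then count as a protocol deviation. Patients who finished treatment before the change would have no scheduled on-treatment TSH, so thyroid event counts before and after it would not be fully comparable; the toxicity report should say so.

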11.0 DATA SUBMISSION SCHEDULE

Case report forms with appropriate source documentation will be completed according to the schedule listed in this section.

Case Report Form	Submission Schedule
Original Consent Form	Prior to registration
On-Study Form	Prior to starting treatment
Treatment Form	Every cycle
Toxicity Form Concomitant Medications Form	Continuous. See Section 7.0 for reporting requirements
Research Tissue Form	Baseline, after Cycle 2/before Cycle 3
Research Blood Form	Baseline, C2D1
Treatment Summary Form	Completion of treatment
Follow Up Form	Every 3 months for 2 years
Death Form	Time of death
RECIST Form	Baseline, end of every even numbered cycle, and end of treatment
MedWatch Form	See Section 7.0 for reporting requirements

11.1 Adverse Event Collection in the Case Report Forms

All adverse events that occur beginning with start of treatment (minus exceptions defined in Section 1.0) must be captured in the Toxicity Form. Baseline AEs should be captured on the Medical History Form.

Participant death due to disease progression should be reported on the Toxicity Form as grade 5 disease progression. If death is due to an AE (e.g. cardiac disorders: cardiac arrest), report as a grade 5 event under that AE. Participant death must also be recorded on the Death Form.

12.0 MEASUREMENT OF EFFECT

12.1 Antitumor Effect – Solid Tumors

For the purposes of this study, patients should be re-evaluated for response every 6 weeks. In addition to a baseline scan, confirmatory scans should also be obtained not less than 4 weeks following initial documentation of objective response.

Response and progression will be evaluated in this study using the new international criteria proposed by the revised Response Evaluation Criteria in Solid Tumors (RECIST) guideline (version 1.1) [Eur J Ca 45:228-247, 2009]. Changes in the largest diameter (unidimensional measurement) of the tumor lesions and the shortest diameter in the case of malignant lymph nodes are used in the RECIST criteria.

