5.0 TREATMENT PLAN

5.1 Agent Administration

Ramucirumab will be given intravenously over the course of an hour on an outpatient basis on Day 1 of each 21-day cycle at a dose of 10 mg/kg.

Atezolizumab will be given intravenously on an outpatient basis on Day 1 of each 21-day cycle at a dose of 1200 mg. The initial dose will be administered over 60 minutes (+/- 15 minutes). If the first infusion is tolerated without infusion-associated events, the second infusion may be delivered over 30 minutes (+/- 10 minutes).

Ramucirumab and atezolizumab may be given in any order on treatment days.

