6.0 DOSE DELAYS/DOSE MODIFICATIONS

6.1 Dose Modifications for Ramucirumab

Treatment modifications for toxicities not listed below will be made at the discretion of the PI. Treatment may be held for a maximum of 6 weeks before a patient must be removed from study treatment. Patients who discontinue ramucirumab must come off study but may continue to receive atezolizumab as standard of care.

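### Tumour assessment is timed every 6 weeks in Section 12.1 but by completed cycles in the calendar and the RECIST form schedule, and no rule says which prevails when a dose is held

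*Combined protocol and SAP*

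**What the plan says.** Three places set the timing of tumour assessment.

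- Section 12.1 uses elapsed time: "patients should be re-evaluated for response every 6 weeks". It gives no starting point, no window and no rule for dose holds.
- Section 10 (Study Calendar) uses cycles. The only on-treatment CT column is headed "End of every 2 cycles". The same section says "Cycles are 21 days long" and "There is a +/- 3 day window for all assessments and procedures".
- Section 11 (Data Submission Schedule) asks for the RECIST form at "Baseline, end of every even numbered cycle, and end of treatment".

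Dosing marks the start of a cycle. Section 5.1 says "Atezolizumab will be given intravenously on an outpatient basis on Day 1 of each 21-day cycle at a dose of 1200 mg", and ramucirumab is given on the same day.

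Two sections allow treatment to be held. Section 6.1 says "Treatment may be held for a maximum of 6 weeks before a patient must be removed from study treatment" and does not say when the 6 weeks start. Section 6.2 says that treatment may be "suspended in patients experiencing toxicity considered to be related to study treatment for up to 60 days after the last dose".

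Section 12.4.5 counts PFS from start of treatment to progression or death, and Section 14.3 describes it by Kaplan-Meier. Neither says how a postponed scan is handled.

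**The concern.** A permitted hold lasts far longer than the 3-day window can absorb. If the held dose pushes back the next Day 1, the end of the second cycle moves with it. Anyone scheduling from the calendar then moves the CT too, while anyone following Section 12.1 scans at week 6. The same patient could get two different progression dates.

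The drift is tied to tolerance: patients held for toxicity are looked at later, and on average this lengthens their recorded PFS. PFS is a secondary endpoint, and Section 1.6.1 cites PFS beyond 6 months in 3 of 12 patients among its reasons for continuing. The timing of the first scan also bears on Section 5.2, which makes a patient non-evaluable for response if treatment stops before Cycle 2 is completed and no disease assessment has been made.

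**Working it through.** **1. Agreement without delays.** 2 cycles x 21 days = 42 days = 6 weeks. The schedules match, and the window gives 39 to 45 days.

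**2. Delay from one maximal hold**, assuming that the held dose stretches the cycle:

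| Limit | Delay d beyond the due dose | Scan interval, 42 + d |
|---|---|---|
| 6.1, 6 weeks counted from the last dose | 42 - 21 = 21 days | 63 days (9 weeks) |
| 6.2, 60 days after the last dose | 60 - 21 = 39 days | 81 days (11.6 weeks) |
| 6.1, 6 weeks counted from the missed dose | 42 days | 84 days (12 weeks) |

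**3. Effect on recorded PFS.** The documents give no PFS assumption for this trial and no hold rate. Assumptions: exponential PFS; a median of 2.3 to 3.9 months (70 to 119 days), borrowed from the Section 1.1 background figures for checkpoint blockers; one hold before the first scan. Progression is dated at the next scan. Let L = ln 2 / median, S(t) = exp(-L t) and q = S(42).

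- Mean recorded time with scans every 42 days: 42 / (1 - q).
- Mean recorded time with the first scan at 42 + d and every 42 days after that: (42 + d) + S(42 + d) x 42 / (1 - q).

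Example, median 70 days and d = 39: L = 0.00990, q = 0.660, and 42 / 0.340 = 123.4 days. Held: 81 + 0.448 x 123.4 = 136.4 days. The shift is about 12.9 days.

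| d | Mean shift in held patients, median 2.3 months | Median 3.9 months |
|---|---|---|
| 21 | 5.7 days | 3.6 days |
| 39 | 12.9 days | 8.2 days |
| 42 | 14.3 days | 9.1 days |

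The range is therefore about 4 to 14 days. With 20% of patients held, the mean over all patients moves by 0.2 x 3.6 = 0.7 to 0.2 x 14.3 = 2.9 days.

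**4. Share recorded progression-free beyond 6 months (182.6 days).** This equals S at the last scan before that date: day 168 on the 6-week grid; day 147 for d = 21 (63 + 84); day 165 for d = 39 (81 + 84); day 168 for d = 42 (84 + 84).

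- d = 21: S(147) - S(168) = 0.233 - 0.189 = 0.044 (median 2.3 months), or 0.424 - 0.375 = 0.049 (3.9 months). With 20% held: 0.9 to 1.0 percentage point.
- d = 39: 0.195 - 0.189 = 0.006, or 0.382 - 0.375 = 0.007. With 20% held: about 0.1 point.
- d = 42: no change.

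**5. Direction for individual patients.** With d = 39, progression by day 42 is dated at day 81, 39 days late. Progression between days 42 and 81 is dated at day 81 instead of day 84, 3 days early. The share dated late is (1 - q) + [S(81) - S(84)] / (1 - q). For a 3-month median (91 days) this is 0.274 + 0.012 / 0.274 = 0.32, so about 68% of held patients are dated 3 days early. The lengthening is an average, driven by early progressors.

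**6. Sensitivity.** A simulation of 400,000 patients placed the hold in the first or second two-cycle block, with 10% to 50% of patients held. Median PFS was unchanged except with 50% held and d = 21 (+0.7 month). The share beyond 6 months rose by 0 to 2.5 points.

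**The case against.** The best defence is that the mechanism is inferred. Section 10 defines a cycle by its length, so two cycles can be read as 42 days whatever happens to dosing. No section says that a held dose delays a cycle rather than skips it, and holding one drug while the other continues need not move the cycle. Section 11 governs form submission, and its end-of-treatment entry may prompt an assessment when a hold ends in discontinuation. This is also a single-institution study, so there is no contrast between sites. All of this stands, and it makes the postponement conditional. It does not remove the conflict: Section 6.0 is headed in terms of dose delays, and nothing says which timing governs when they diverge.

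A reader might infer more than the documents support:

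- **That recorded PFS is seriously inflated.** One could note that, with 20% held to day 81 and a 3-month median, the share recorded progression-free beyond day 42 rises from 73% to 78%. That follows directly from held patients having no scan before day 81 (0.8 x 0.726 + 0.2 x 1 = 0.78) and says little about the curve as a whole.
- **That the decision to continue rested on delayed scans.** Section 1.6.1 also cites tumour reduction in 8 patients and good tolerance, and describes the 3 patients as still on treatment. Nothing suggests that holds produced their PFS.
- **That the ORR denominator is compromised.** Under Section 5.2 a late scan alone removes nobody. The exposed case is narrow: a patient held early who stops after week 6 without a scan. The end-of-treatment RECIST form is a partial safeguard, since the calendar shows no CT in its end-of-treatment column.
- **That Section 12.1 already fixes scans regardless of holds.** It gives an interval only.

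**Conclusion.** The inconsistency is real and its consequence is modest. If a held dose stretches the cycle and staff follow the calendar, the next scan comes 21 to 42 days late, and progression that the week-6 scan would have shown is dated late. The average shift of about 4 to 14 days in held patients, and the rise of 0 to about 1 percentage point in the share beyond 6 months, rest on the assumed exponential PFS, the borrowed medians, one maximal hold before the first scan and, for the second figure, an assumed 20% held. Section 1.6.1 reports good tolerance, so long holds may be few.

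PFS is secondary, single-arm and descriptive, and no decision rule uses it. The effect on ORR is negligible. Severity is minor. Confidence that the text conflicts is high; confidence in the size of the effect is moderate.

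**What to change.** Reconcile Sections 10, 11 and 12.1. In the calendar's CT column and the RECIST form row, state that tumour assessments occur every 6 weeks (+/- 3 days) counted from Cycle 1 Day 1, regardless of dose delays. This keeps the Section 12.1 interval and adds the anchor and hold rule that it lacks; repeat the sentence there.

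Two places need matching edits:

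- Section 5.2: align the wording on completing Cycle 2 with the week-6 assessment.
- Section 9.2, calendar footnote 4 and the Research Tissue Form row in Section 11: these place the repeat biopsy after the CT between Cycles 2 and 3. Make them consistent with a scan at week 6.

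The hold limits in Section 6 need no change for this purpose. The cost is a few lines of text. The downside is that, after a hold, scan, dosing and biopsy visits may no longer coincide.
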